#### 4.3.4 VISIT 3: 4-Week Post-Treatment and Final Visit

**Visit 3** will take place  **$30 \pm 7$  days** from Visit 2. Subjects will be assessed to quantify changes in metabolic fuel utilization after treatment with empagliflozin. These changes are determined based on metabolomic profiling of acyl-carnitines, organic acids and amino acids and indirect calorimetry measurements. The list of procedures performed is listed in **Table 1**.

Subjects will take their final dose of study medication on the day of visit 3. Subjects will be asked to bring all trial medication containers (with or without any remaining tablets) with them to visit 3. Subjects who forget to return trial medication containers will be asked to bring them at a separate visit. The tablets will be counted by the PI, Co-I or study team members and compliance will be calculated according to the formula:

$$\text{Compliance (\%)} = \frac{\text{Number of tablets actually taken since visit 2}}{\text{Number of tablets which should have been taken in the same period}} \times 100\%$$

In addition, study subjects will be asked to fill up a Subject Treatment Diary to record the number of doses of empagliflozin 10mg taken. The Subject Treatment Diary will be reviewed by the PI, Co-I or study team member at visit 3.

The study drug will be discontinued upon completion of visit 3, and any remaining study drug tablets will be returned to the study team.

Should study subjects misplace any empagliflozin 10mg tablets between visit 2 and visit 3, the exact number of misplaced tablets will be resupplied to them by the study team.

Study drug will be discontinued for subjects upon occurrence of any adverse drug reaction to empagliflozin.

#### **4.3.5 Post Study Follow up and Procedures**

Subjects will continue their routine follow-up with their regular physicians upon completion of the final study visit. There will be no post study follow-up procedures.

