**F) Fournier's gangrene**

On 29th August 2018, the U.S. Food and Drug Administration (FDA) warned that cases of a rare but serious infection of the genitals and area around the genitals have been reported with SGLT2 inhibitors. This serious rare infection, called necrotizing fasciitis of the perineum, is also referred to as Fournier's gangrene. In the five years from March 2013 to May 2018, 12 cases of Fournier's gangrene were identified in patients taking an SGLT2 inhibitor (7 men and 5 women), all of whom were hospitalized and required surgery. In 2017, an estimated 1.7 million patients received a dispensed prescription for an SGLT2 inhibitor from U.S. outpatient retail pharmacies. Fournier's gangrene developed within several months of the patients starting an SGLT2 inhibitor. In accordance with recommendations made by the U.S. FDA, patients will be counselled regarding the risk of Fournier's gangrene before commencing treatment with empagliflozin. Patients will be counselled to seek medical attention immediately if they experience any symptoms of tenderness, redness, or swelling of the genitals or the area from the genitals back to the rectum, and have a fever above 38.0 degrees Celsius, or a general feeling of being unwell.

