**Table 1. Study Procedures**

	Visit 1	Visit 2	Visit 3
	Consent & Screening	Dosing & Metabolic Evaluation	Post-treatment and Final Visit
Administrative			
Informed consent	X		
Inclusion/Exclusion criteria	X		
Dispense Medication		X	
Monitoring of drug compliance			X
Clinical Procedures/Assessment			
Fasting ( $\geq 8$ hours)		X	X
Medical History/Assessment	X		X
Drug History	X		X
Adverse Effects Monitoring			X
General Physical Examination	X		X
BP/Pulse	X		X
Weight (triplicate) *	X		X
Height (triplicate) *	X		
Hip/Waist Circumference (triplicate) **	X		X
Indirect Calorimetry ***		X	X
Laboratory Procedures			
HbA1C	X		
Fasting Glucose		X	X
Full Blood Count	X		
Potassium	X		X

Creatinine	X		X
eGFR Calculation	X		X
Lipid Panel		X	X
Urine $\beta$ HCG (female of child bearing potential)	X	X	
ALT	X		X
AST	X		X
Metabolomic Profiling		X	X
Urine ACR	X		X
Urine PCR		X	X

\* Weight will be measured in light clothing to the nearest 0.1 kg on a balance scale and height with a stadiometer three times and then averaged

\*\* Waist circumference will be measured from the inferior margin of the last rib and hip circumference measured at the crest of the ileum to the nearest 0.1 cm three times and averaged

\*\*\* Indirect calorimetry using a canopy hood will be performed for 30 minutes for measurement of basal energy expenditure, CO2 production and O2 consumption

ALT = Alanine Transaminase

AST = Aspartate Transaminase

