#### 4.3.3 VISIT 2: Initiation of Study Drug

Subjects who satisfy the inclusion and exclusion criteria will return to the CTRC within the next **14 days** for **visit 2** to receive the study drug, empagliflozin. Empagliflozin 10mg daily is to be taken orally for  $30 \pm 7$  days. Subjects will take the first dose of empagliflozin under supervision of the clinical research coordinator at SGH CTRC.

Patients will be instructed to take empagliflozin once daily with water. To ensure a dose interval of about 24 hours, the medication should be taken at the same time every day, with or without food. If a dose is missed by more than 12 hours, that dose should be skipped and the next dose should be taken as scheduled. No double doses should be taken, and dose reductions are not permitted.

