### **4.4.2 Discontinuation Visit and Procedures**

Should any suspected study drug-related adverse effects occur, study subjects may contact the study coordinator. If required, they would be scheduled for a visit at SGH CTRC within the next 72 hours. They will be assessed by a member of the study team who is a registered medical practitioner for their suitability to continue with the study drug. Subjects may be referred back to their primary physician or other physicians as necessary upon the discovery of any drug-related adverse reaction to be given appropriate care under medical supervision until the symptoms of any adverse event resolve, or the subject's condition becomes stable. In the event of any medical emergency or urgency, subject will be referred to the Emergency Department.

Subjects who have taken at least one dose of the study drug and withdrew from this study (voluntary withdrawal or discontinuation due to adverse reaction), are encouraged to return for their third visit ( $30 \pm 7$  days from Visit 2) any and complete all planned study procedures as listed in **Table 1**. Subjects who had not taken any study drug will not be required to return for any subsequent study visits.

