## **7.4 Safety Monitoring Plan**

Any adverse effects will be reported. The PI and Co-investigators will monitor and report to the CIRB and HSA of any SAE. There will be no DSMB. Risks of study drug will be continually reassessed throughout the study period. Closed monitoring meetings with the research team will take place every 4 weeks to discuss the data collected from monitoring reports.

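### Adverse effects are scheduled to be asked about once, on the day of the last dose, and section 4.3.5 rules out any study procedure afterwards, in conflict with two follow-up duties set elsewhere

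*Protocol*

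**What the plan says.** - **Schedule.** In Table 1 the row "Adverse Effects Monitoring" has one mark, under Visit 3. There is none under Visit 2, although section 4.3.3 has the first dose taken there under supervision.
- **Exposure.** Section 4.3.3: "Empagliflozin 10mg daily is to be taken orally for" 30 ± 7 days. Section 4.3.4 sets Visit 3 at the same distance from Visit 2 and adds: "Subjects will take their final dose of study medication on the day of visit 3".
- **After Visit 3.** Section 4.3.5: "Subjects will continue their routine follow-up with their regular physicians upon completion of the final study visit". It then states: "There will be no post study follow-up procedures".
- **Unscheduled reporting.** Section 6.3 has subjects warned about listed symptoms and told to contact the coordinator. Section 4.4.2 lets them make contact and offers a visit within 72 hours if required.
- **Duties that can outlast Visit 3.** Section 4.4.1 has a pregnancy arising in the trial followed to its end. Section 7.3 has follow-up information on reported SAEs pursued and submitted, with no end date.
- **Oversight.** Section 7.4 provides for no DSMB, has the team meet every 4 weeks, and says: "Risks of study drug will be continually reassessed throughout the study period".

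**The concern.** Section 4.3.5 does more than leave a detail open. It fixes the scheduled safety window after the last dose at nothing. An infection or volume effect that begins with the last tablets, or in the days after, has no scheduled point at which anyone asks about it. An abnormal Visit 3 laboratory value may come back after the subject has left, and the protocol does not say who looks at it or what is recorded next.

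The reporting timelines in sections 7.2 and 7.3 start only when the investigator learns of an event, so they depend on this capture. Section 2.4.2 tells subjects that direct benefit is unlikely, which adds weight to recording harm completely. The statement in section 4.3.5 also leaves staff with conflicting instructions when a pregnancy or an SAE is still open at the final visit.

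**Working it through.** The plan gives no figure to reproduce. The check is a comparison of passages with one small calculation.

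**1. Scheduled window**
- Inputs: treatment and Visit 3 timing of 30 ± 7 days (sections 4.3.3 and 4.3.4); last dose on the day of Visit 3 (4.3.4); adverse-effect mark at Visit 3 only (Table 1); nothing afterwards (4.3.5).
- First dose to the only scheduled query: 30 − 7 = 23 days to 30 + 7 = 37 days.
- Last dose to the end of scheduled collection: Visit 3 day − Visit 3 day = 0 days.
- This holds for subjects who complete treatment. Section 4.4.2 encourages those who stop early to return for Visit 3, so they may have some observation after their last dose.

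**2. What else could capture events**
- Sections 4.4.2 and 6.3 give a route that the subject must start. No end date is attached to it, but no text extends it past Visit 3 either.
- The treatment diary (4.3.4) is described only as a record of doses taken.
- Together these leave spontaneous reporting as the only route for an event that begins after Visit 3.

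**3. Visit 3 laboratory results**
- Section 4.3.2 names who reviews screening results. Section 4.3.4 names who counts tablets and reviews the diary. Neither names a reviewer for Visit 3 laboratory results.
- Section 4.4.1 includes a creatinine rise of more than 50% from baseline among the reasons to stop the drug. Table 1 measures creatinine only at Visits 1 and 3. On the schedule, the first value that could show the rise is therefore taken on the day treatment ends anyway, and no recheck is scheduled.

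**4. Section 4.3.5 against the rest**

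| Section | What it requires | Fit with no procedures after the study |
|---|---|---|
| 4.4.1, pregnancy | Follow-up to birth or other end of the pregnancy | Conflict: this runs well past Visit 3. The last scheduled pregnancy test is at Visit 2, so detection could also come late |
| 7.3, SAEs | Follow-up information to be pursued | Conflict if the SAE is open at Visit 3: no mechanism or end date is given |
| 4.4.2, adverse reactions | Possible referral to other physicians for care "until the symptoms of any adverse event resolve, or the subject's condition becomes stable" | Compatible: permissive wording, and the care is given outside the study |

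**The case against.** The case against has real force in several places.

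- **A reader might infer that section 4.4.2 promises follow-up and so contradicts section 4.3.5.** It does not. It says that subjects may be referred where necessary and that other physicians provide the care, which agrees with the first sentence of section 4.3.5. What it leaves open is who records the outcome for the study.
- **A reader might infer from section 2.4.1 F that the trial stops watching too early for Fournier's gangrene.** The text reads: "Fournier's gangrene developed within several months of the patients starting an SGLT2 inhibitor". That is time from starting the drug class. It says nothing about onset after a course of about a month has stopped. Coverage cannot be calculated either, because the protocol does not say how long several months is: assuming 2 to 6 months, it runs from 37/61 = 61% down to 23/183 = 13%. The event is also very rare. Crudely, 40 × 12/1,700,000 ≈ 0.0003 cases would be expected in 40 subjects, with the 12 cases spread over about five years and the 1.7 million patients counted in one. The point does not rest on this event.
- **A reader might infer that there is no safety capture between visits, or that the reassessment in section 7.4 uses only data gathered once exposure is over.** The symptom warnings and coordinator contact apply during treatment, Visit 3 itself falls on a treatment day, and team meetings every 4 weeks inform the care of later subjects.
- **Open events are not all lost.** Section 7.3 covers follow-up of SAEs reported to HSA. Nothing says that Visit 3 results go unreviewed; section 4.3 sends samples for immediate analysis. The gap is that no one is assigned.
- **Section 4.3.5 may be meant only for routine procedures, with pregnancy and SAEs as exceptions.** That is a plausible intention, but the text does not say so.
- **Proportion.** The single objective is metabolic, no safety endpoint is set, and the drug is given at its labelled starting dose. This limits the weight of the point. It does not remove the gap.

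**Conclusion.** The point holds in limited form. Scheduled adverse-effect collection is a single query 23 to 37 days after the first dose and 0 days after the last, for subjects who complete treatment. Later events depend on the subject volunteering them, and no one is assigned to act on Visit 3 laboratory results. Section 4.3.5, read as written, conflicts with sections 4.4.1 and 7.3. It is compatible with section 4.4.2.

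The documents do not allow an estimate of how many events would be missed, because they give no rates for onset after stopping, and none is claimed here. The primary metabolic comparison is not affected. The change is worth making because it is cheap and because an explicit rule, rather than an omission, creates the gap.

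**What to change.** - **Section 4.3.5:** state an AE/SAE collection period after the last dose, of a length the sponsor sets, closed by one scripted telephone contact from the existing coordinator.
- **Table 1:** mark adverse-effect monitoring at Visit 2 after the supervised first dose, and add the telephone contact.
- **Reconciliation:** bring section 4.3.5 into line with sections 4.4.1, 4.4.2 and 7.3, so that it is clear who reviews Visit 3 results and who records events that are open at Visit 3 or start after it. How those events are managed clinically is for the sponsor to decide.

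**Cost:** one call for each of 40 subjects, about 40 calls; some CRF lines; and a protocol amendment. No scheduled visit, sample or staff member is added, and no dose or stopping rule changes.

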## **4.4 Discontinuation/Withdrawal**

### **4.4.1 Discontinuation Criteria**

Study drug will be discontinued following completion of visit 3 (final study visit).

Study drug will be discontinued upon the development of any of the following adverse reactions:

1. Any allergic reaction to study drug
2. An increase in creatinine by > 50% compared to baseline
3. Ketoacidosis
4. Urosepsis and pyelonephritis
5. Fournier's gangrene

Individual patients will also be withdrawn from the trial if:

1. The patient withdraws consent, without the need to justify the decision.
2. If a patient becomes pregnant during the trial, the investigational drug will be stopped, the patient will be discontinued from treatment, and the patient will be followed up until birth or otherwise termination of the pregnancy.

All patients who drop out of the study after visit 1 (Consent & Screening), but before visit 2 (Dosing) will be considered a screening failure, and no further follow-up is required.

### **4.4.2 Discontinuation Visit and Procedures**

Should any suspected study drug-related adverse effects occur, study subjects may contact the study coordinator. If required, they would be scheduled for a visit at SGH CTRC within the next 72 hours. They will be assessed by a member of the study team who is a registered medical practitioner for their suitability to continue with the study drug. Subjects may be referred back to their primary physician or other physicians as necessary upon the discovery of any drug-related adverse reaction to be given appropriate care under medical supervision until the symptoms of any adverse event resolve, or the subject's condition becomes stable. In the event of any medical emergency or urgency, subject will be referred to the Emergency Department.

Subjects who have taken at least one dose of the study drug and withdrew from this study (voluntary withdrawal or discontinuation due to adverse reaction), are encouraged to return for their third visit ( $30 \pm 7$  days from Visit 2) any and complete all planned study procedures as listed in **Table 1**. Subjects who had not taken any study drug will not be required to return for any subsequent study visits.

## **5 TRIAL MATERIALS**

### **5.1 Trial Product (s)**

Information on trial product (empagliflozin 10mg) is detailed in the prescribing information attached in Appendix 2.

## **5.2 Storage and Drug Accountability**

Empagliflozin (Jardiance) will be stored in the original package in order to protect from light and moisture, at a room temperature not exceeding 30 °C. It will be stored securely in the investigator product cabinet at the SGH CTRC IP Room with restricted access. Study drug will be stored securely and the study coordinator will maintain a dispensing log. IP will be monitored by a 24-hour Temperature Monitoring System (TMS) and reports will be generated on a fortnightly basis. Alarms to any excursion will be triggered and the CTRC staff and FRS will be informed.

## **6 TREATMENT**

### **6.1 Rationale for Selection of Dose**

Dosage of empagliflozin is similar to that used for the treatment of type 2 diabetes mellitus in clinical practice. Eligible subjects will be given empagliflozin 10mg once daily to be taken orally for 30 ± 7 days.

### **6.2 Study Drug Formulations**

Study drug will be dispensed as empagliflozin (Jardiance) 10mg film-coated tablets.

### **6.3 Study Drug Administration**

Study drug is to be taken orally. Subjects will be warned to look out for the following symptoms and contact the study coordinator if they occur:

- a) Development of allergic reactions (eg: new rash)
- b) Symptoms suggestive of hypotension (eg: light-headedness)
- c) Symptoms suggestive of ketoacidosis (eg: nausea, vomiting, abdominal pain, generalized malaise, shortness of breath)
- d) Factors predisposing to ketoacidosis which may warrant discontinuation of empagliflozin (eg: acute febrile illness, reduced caloric intake due to illness or surgery)
- e) Factors predisposing to acute kidney injury which may warrant discontinuation of empagliflozin (eg: reduced oral intake, fluid losses)
- f) Symptoms suggestive of urinary tract infection (eg: fever, dysuria) and genital mycotic infection (eg: genital discharge or pruritus)
- g) Symptoms suggestive of Fournier's gangrene (eg: fever, malaise, or tenderness, redness, or swelling of the genitals or the area from the genitals back to the rectum)

## **6.4 Specific Restrictions / Requirements**

Individuals who are treated with insulin or in whom insulin treatment is clinically indicated will be excluded from this study.

## **6.5 Blinding**

This is an open-label study.

## **6.6 Concomitant therapy**

All medications (prescription and over the counter), vitamin and mineral supplements, and / or herbs taken by the participant will be documented.

# **7 SAFETY MEASUREMENTS**

## **7.1 Definitions**

An adverse event (AE) is any untoward medical occurrence in a patient or clinical investigation subject administered a pharmaceutical product and which does not necessarily have a causal relationship with this treatment.

A serious adverse event (SAE) or reaction is any untoward medical occurrence that at any dose:

- results in or contributes to death
- is life-threatening
- requires inpatient hospitalisation or prolongation of existing hospitalisation
- results in or contributes to persistent or significant disability/incapacity or
- results in or contributes to a congenital anomaly/birth defect
- results in such other events as may be prescribed
- is a medical event that may jeopardize the patient and may require medical or surgical intervention to prevent one of the outcomes listed above.

## **7.2 Collecting, Recording and Reporting of Adverse Events and Serious Adverse Events to CIRB**

Reporting of adverse events involves the PI submitting to the approving CIRB the completed SAE Reporting Form within the stipulated timeframe. PI is responsible for informing the institution representative (local SAE resulting in death), sponsor or regulatory bodies as required and appropriate.

Reporting timeline to CIRB:

- SAE that result in death, regardless of causality, should be reported immediately - within 24 hours of the PI becoming aware of the event.
- Local life-threatening (unexpected/ expected) SAE should be reported no later than 7 calendar days after the Investigator is aware of the event, followed by a complete report within 8 additional calendar days.
- Local unexpected SAE that are related events, but not life-threatening, should be reported no later than 15 calendar days after the investigator is aware of the event.
- An increase in the rate of occurrence of local expected SAE, which is judged to be clinically important, should be reported within 15 calendar days after the PI is aware of the event.
- Local expected SAE should be reported annually (together with Study Status Report for annual review).
- Local unexpected and unlikely related SAE that are not life-threatening should also be reported annually (together with Study Status Report for annual review).
- Local unexpected AE that are related events should be reported at least annually (together with Study Status Report for annual review).
- Non-local unexpected SAE that are fatal or life threatening and definitely/probably/possibly related should be reported not later than 30 calendar days after the PI is aware of the event.

## **7.3 Collecting, Recording and Reporting of Serious Adverse Events (SAEs) to the Health Science Authority (HSA)**

All SAEs that are unexpected and related to the study drug will be reported to HSA. All SAEs will be reported to HSA. Please refer to the HSA website for more information on Safety Reporting Requirements for Clinical Trials.

The investigator is responsible for informing HSA no later than 15 calendar days after first knowledge that the case qualifies for expedited reporting. Follow-up information will be actively sought and submitted as it becomes available. For fatal or life-threatening cases, HSA will be notified as soon as possible but no later than 7 calendar days after first knowledge that a case qualifies, followed by a complete report within 8 additional calendar days.

## **7.4 Safety Monitoring Plan**

Any adverse effects will be reported. The PI and Co-investigators will monitor and report to the CIRB and HSA of any SAE. There will be no DSMB. Risks of study drug will be continually reassessed throughout the study period. Closed monitoring meetings with the research team will take place every 4 weeks to discuss the data collected from monitoring reports.

